#### 7.2 ADHERENCE TO THE CLINICAL INVESTIGATION PLAN

A deviation is defined as an event where the clinical investigator, site personnel, sponsor or sponsor representative did not conduct the clinical study according to the Clinical Investigational Plan, EC requirements or the Investigator Agreement. The investigator is not allowed to deviate from the CIP, except as specified under emergency circumstances.

In some cases, failure to comply with the CIP may be considered failure to protect the rights, safety and well-being of subjects, since the non-compliance exposes subjects to unreasonable risks. For example, failure to adhere to the inclusion/exclusion criteria: these criteria are specifically defined by the Sponsor to exclude subjects for whom the device is not beneficial and the use involves unreasonable risks. This may be considered failure to protect the rights, safety and well-being of the enrolled subject. Similarly, failure to perform safety assessments intended to detect adverse events may be considered failure to

## Clinical Investigational Plan

protect the rights, safety and well-being of the enrolled subject. Investigators should seek minimization of such risks by adhering to the CIP.

Simultaneously, in the event that adhering to the CIP might expose the subject to unreasonable risks, the investigator is also required to protect the rights, safety and well-being of the subject by intentionally deviating from the requirements of the CIP, so that subjects are not exposed to unreasonable risks.

It is the responsibility of the investigator to provide adequate medical care to a subject enrolled in a study.

Regulations require that the PI maintain accurate, complete, and current records, including documents showing the date of and reason for every deviation from the Clinical Investigational Plan. Relevant information for each deviation will be documented on a Deviation Case Report Form. The site will submit the CRF to St. Jude Medical.

Regulations require Investigators obtain approval from St. Jude Medical and the EC [as required] before initiating changes in or deviations from the protocol, except when necessary to protect the life or physical well-being of a subject in an emergency.

Prior approval must be requested when the PI anticipates, contemplates, or makes a conscious decision to depart from the CIP, except when unforeseen circumstances are beyond the investigator's control (e.g. a subject who fails to attend a scheduled follow-up visit, a subject is too ill to perform a CIP-required test, etc.). All deviations, including those beyond the investigator's control, must be reported on a CRF.

To obtain approval, the Principal Investigator may call or email and discuss the potential deviation with St. Jude Medical or designee prior to initiating any changes.

All deviations must be reported to appropriate regulatory authorities in specified timelines (if appropriate).

### 7.3 REPEATED AND SERIOUS NON-COMPLIANCE

In the event of repeated non-compliance or a one-time serious non-compliance, as determined by the Sponsor, a Clinical Research Associate or clinical representative will attempt to secure compliance by one or more of the following actions:

- Visiting the investigator
- Contacting the investigator by telephone
- Contacting the investigator in writing
- Retraining of the investigator

If an investigator is found to be repeatedly non-compliant with the signed agreement, the CIP or any other conditions of the clinical study, the Sponsor will either secure compliance or, at its sole discretion, terminate the investigator's participation in the clinical study.

## Clinical Investigational Plan

### 8.0 ADVERSE EVENT, ADVERSE DEVICE EFFECT, DEVICE DEFICIENCY

#### 8.1 DEFINITIONS

##### 8.1.1 Medical device

Any instrument, apparatus, implement, machine, appliance, implant, software, material or other similar or related article

- Intended by the manufacturer to be used, alone or in combination, for human beings for one or more of the specific purpose(s) of
  - Diagnosis, prevention, monitoring, treatments or alleviation of disease,
  - Diagnosis, monitoring, treatment, alleviation of, or compensation for, an injury,
  - Investigation, replacement, modification, or support of the anatomy or of a physiological process,
  - Supporting or sustaining life,
  - Control of conception,
  - Disinfection of medical devices and
- Which does not achieve its primary intended action in or on the human body by pharmacological, immunological or metabolic means, but which may be assisted in its intended function by such means

##### 8.1.2 Adverse Event (AE)

Any untoward medical occurrence, unintended disease or injury, or untoward clinical signs (including abnormal laboratory findings) in subjects, users or other persons, whether or not related to the medical device under study.

This definition includes events related to the medical device.

##### 8.1.3 Serious Adverse Event (SAE)

An adverse event that led to:

- Death
- A serious deterioration in the health of the subject, that either resulted in:
  - A life-threatening illness or injury OR
  - A permanent impairment to a body structure or a body function OR
  - An in-patient or prolonged hospitalization OR
  - A medical or surgical intervention to prevent life-threatening illness or injury or permanent impairment to a body structure or a body OR
  - A malignant tumor
- Fetal distress, fetal death or a congenital abnormality or birth defect

A planned hospitalization for a pre-existing condition, or a procedure required by the CIP is not considered a serious adverse event.

## Clinical Investigational Plan

### 8.1.4 Adverse Device Effect (ADE)

An adverse event related to the use of a medical device.

This definition includes adverse events resulting from insufficient or inadequate instructions for use, deployment, implantation, installation, or operation, or any malfunction of the medical device.

This definition includes any event resulting from the use error or from intentional misuse of the medical device.

### 8.1.5 Serious Adverse Device Effect (SADE)

Adverse device effect that has resulted in any of the consequences characteristic of a serious adverse event.

#### 1. Unanticipated Serious Adverse Device Effect (USADE) [applicable to studies following ISO 14155]

A serious adverse device effect which by its nature, incidence, severity or outcome has not been identified in the current version of the risk analysis report.

#### 2. UADE [applicable to investigational studies following FDA regulations]

As defined in 21 CFR §812.3, unanticipated adverse device effects (UADE) are defined as any serious adverse effect on health or safety or any life-threatening problem or death caused by, or associated with, a device, if that effect, problem, or death was not previously identified in nature, severity, or degree of incidence in the clinical investigational plan or application (including a supplementary plan or application), or any other unanticipated serious problem associated with a device that relates to the rights, safety, or welfare of subjects.

If an unanticipated adverse device effect occurs, the investigator must notify St. Jude Medical and the IRB/MEC immediately, but no later than 10 working days of the investigator's knowledge of the event, as required by 21 CFR §812.150. St. Jude Medical will take any steps necessary to investigate the event, and will be responsible for notifying FDA and all other participating IRBs/MECs and investigators.

#### 3. Anticipated Serious Adverse Device Effect (ASADE)

A serious adverse device effect which by its nature, incidence, severity or outcome has been previously identified in the risk analysis report.

### 8.2 PROCEDURE FOR ASSESSING, RECORDING, AND REPORTING ADVERSE EVENTS, DEVICE DEFICIENCIES/COMPLAINTS, ADVERSE DEVICE EFFECTS, SERIOUS ADVERSE EVENTS, AND SERIOUS ADVERSE DEVICE EFFECTS:

Safety surveillance within this study and the safety reporting both performed by the investigator, starts as soon as the subject is enrolled in this study (date of signature of the informed consent). The safety surveillance and the safety reporting will continue until the last investigational visit has been performed, the subject is deceased, the subject/investigator concludes his participation into the study or the subject/investigator withdraws the subject from the study, except as otherwise specified in the CIP.

## Clinical Investigational Plan

All adverse event data including deaths will be collected throughout the clinical study and will be reported to the Sponsor on a dedicated case report form or through the EDC system. The Investigator will record all adverse events and device deficiencies on the appropriate case report forms.

Records relating to the subject's subsequent medical course must be maintained and submitted (as applicable) to the Sponsor until the event has subsided or, in case of permanent impairment, until the event stabilizes and the overall clinical outcome has been ascertained. Adverse events will be monitored until they are adequately resolved. The status of the subject's condition should be documented at each visit.

The investigator will report the event to the EC per their reporting requirements.

Reportable events to sponsor are considered:

- All Adverse Device Effects
- All Serious Adverse Events

All above events will be reported to the Sponsor, as soon as possible, but no later than 72 hours of first learning of the event.

There are no additional anticipated adverse events associated with the use of devices utilized in this study that are different than those currently identified for the commercially available neurostimulation systems.

Additional information may be requested, when required, by the Sponsor in order to support the reporting of AEs to regulatory authorities.

The investigator must notify the EC, if appropriate, in accordance with national and local laws and regulations, of the AEs reported to the Sponsor.

All adverse events will be reported as per applicable regulatory requirements.

### 8.3 SUBJECT DEATH

#### 8.3.1 Procedure for recording and reporting subject death

All subject deaths are to be documented and reported to the sponsor within 72 hours after becoming aware of the event.

### 9.0 DATA MANAGEMENT

Overall, the Sponsor will be responsible for the data handling.

Data will be analyzed by the Sponsor and may be transferred to the Sponsor's locations outside of Europe and/or any other worldwide regulatory authority in support of a market-approval application.

## Clinical Investigational Plan

St. Jude Medical respects and protects personally identifiable information that we collect or maintain. As part of our commitment, St. Jude Medical is certified to the U.S. - European Union Framework and U.S. – Swiss Safe Harbor Framework Agreements regarding human resources and subject clinical trial personal information. The privacy of each subject and confidentiality of his/her information will be preserved in reports and when publishing any data. Confidentiality of data will be observed by all parties involved at all times throughout the clinical study. All data will be secured against unauthorized access.

During the study Clinical Report Forms will be produced to record primary and secondary outcome measures. All the clinical report forms (including informed consent, inclusion/exclusion criteria, user satisfaction and randomization) will be translated in the language used in each of the countries where the study sites will be located.

The Principal Investigator or institution will provide direct access to source data during and after the clinical study for monitoring, audits, EC review and regulatory authority inspections. As required, the Principal Investigator or institution will obtain permission for direct access to source documents from the subject, hospital administration and national regulatory authorities before starting the clinical study.

### 9.1 DATA MANAGEMENT PLAN

Data are captured on paper CRFs which are verified and signed by the Principal Investigator or his/her designee. Paper CRFs will be electronically sent to SJM and then captured in a validated electronic database management system hosted by St. Jude Medical.

All CRF received data for the study will be entered by trained and qualified St. Jude Medical personnel. An electronic audit trail will be used to track any subsequent changes of the entered data.

### 9.2 DOCUMENT AND DATA CONTROL

#### 9.2.1 Traceability of documents and data

The investigator will ensure accuracy, completeness, legibility and timeliness of the data reported to the sponsor on the CRFs and in all required reports.

#### 9.2.2 Recording data

Source documents will be created and maintained by the investigational site team throughout the clinical study.

The data reported on the CRFs will be derived from, and be consistent with, these source documents, and any discrepancies will be explained in writing.

The following data can be recorded directly in the CRFs:

- Pain VAS scores
- EQ-5D scores
- Subjects satisfaction
- Subject preference

## Clinical Investigational Plan

- Stimulation parameters

The CRFs will be signed and dated by the authorized site personnel. Any corrections should be made by scoring through the original value with a single line and writing the new value next to the original entry with the authorized personnel initialing and dating the new entry. Only the authorized personnel may amend or otherwise alter any data documented onto the CRF. In addition, any changes must be made on all copies of the document so that there is no difference between copies. If the reason for the correction is not obvious then, when appropriate, a brief explanation of the reason for the correction should be made. Correction fluids should never be used on any document. Before forwarding copies of completed CRFs to SJM, the Investigator/Appointed Staff Members should review their completeness, accuracy and legibility. The Investigator must always retain a copy of all completed CRFs in their file.

For CRFs that have been submitted to the Sponsor, no corrections or alterations are to be made on the CRF. Any correction, alteration, or clarification must be documented on a Data Clarification Form (DCF) and signed by the Investigator or designated staff.

### 10.0 MONITORING

It is the responsibility of St. Jude Medical as the sponsor of the study to ensure the study is conducted, recorded, and reported according to the approved protocol, subsequent amendment(s), applicable regulations, and guidance documents. Monitoring will be conducted according to the St. Jude Medical Clinical Monitoring standard operating procedure.

Prior to beginning the study, St. Jude Medical will contact the investigator or designee to discuss the study and data requirements. A St. Jude Medical monitor will periodically review the subject records and associated source documents.

On-site monitoring may occur at the discretion of the sponsor. If on-site monitoring is utilized, a St. Jude Medical monitor will review the subject records and associated source documents on-site. The investigator shall make subject and study records available to the clinical monitor for monitoring.

Centralized monitoring will occur through routine internal data review. This monitoring is designed to identify missing and inconsistent data, data outliers, and potential protocol deviations that may be indicative of site non-compliance.

### 11.0 REGULATORY INSPECTIONS

The investigator and/or delegate should contact St. Jude Medical immediately upon notification of a governmental agency inspection at the site. A clinical monitor or designee will assist the investigator and/or delegate in preparing for the audit.

An investigator who has authority to grant access will permit authorized governmental agency employees, at reasonable times and in reasonable manner, to enter and inspect any establishment where devices are held (including any establishment where devices are used or where records or results are kept).

## Clinical Investigational Plan

An investigator, or any person acting on behalf of such a person with respect to the study, will permit authorized governmental agency employees, at reasonable times and in reasonable manner, to inspect and copy all records relating to the study.

An investigator will permit authorized governmental agency employees to inspect and copy records that identify subjects, upon notice that governmental agency has reason to suspect that adequate informed consent was not obtained, or that reports required to be submitted by the investigator, to the Sponsor or EC have not been submitted or are incomplete, inaccurate, false or misleading.

### 12.0 STATISTICAL CONSIDERATIONS

#### 12.1 STATISTICAL DESIGN, HYPOTHESES, METHOD AND ANALYTICAL PROCEDURES

During baseline visit subjects will be randomized 1:1:1 to one of the three treatment sequences. An envelope-based system will be used for identifying which group the subject has been assigned. St. Jude Medical will provide sealed envelopes containing the site number and subject ID/sequence number. Inside the envelope, the randomization assignment will be identified along with the site number and subject ID/sequence number.

During reprogramming the subjects will not be made aware of what paradigm is currently being programmed. Pain questionnaires (VAS, EQ-5D, satisfaction and stimulation preference) will be administered by a clinician blinded to the currently programmed stimulation paradigm.

Scores from the subject's questionnaires as well as subject satisfaction will be compared between follow up visits using a repeated measure ANOVA under the hypothesis of equivalence between standard and burst microdosing stimulation paradigms.

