### Clinical Investigational Plan

#### 1.0 SYNOPSIS

Title:	Burst Optimized Stimulation Study
Acronym:	BOSS
Purpose:	This purpose of this study is to evaluate the therapeutic efficacy of energy efficient burst microdosing stimulation paradigms in patients with chronic pain.
Primary Objectives:	To compare differences in therapeutic efficacy between conventional burst stimulation parameters (Burst train consisting of 5 pulses, Intraburst frequency: 500 Hz, Burst Rate: 40 Hz, Pulse width: 1000 μs) and energy efficient burst microdosing stimulation paradigms listed below: 
 
• Standard burst stimulation parameters with 5 seconds of STIM ON, followed by 5 seconds of STIM OFF
 
• Standard burst stimulation parameters with 5 seconds of STIM ON, followed by 10 seconds of STIM OFF
 

Secondary Objectives:	To compare differences in: 
 
• Quality of life
 
• Subject satisfaction
 
• Patient preference
 
• Incidence of adverse events
 
 
between standard burst stimulation and the two different burst microdosing paradigms.

Primary Endpoints:	
 
• Change in Visual Analog Scale (VAS) between baseline and follow up visits
 

Secondary Endpoints	Difference in 
 
• Quality of life (EQ-5D)
 
• Subject satisfaction
 
• Incidence rate of adverse events
 
 
between standard burst stimulation and the two different burst microdosing paradigms

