### Clinical Investigational Plan

	
After two weeks, subjects will return for the third follow up visit and complete questionnaires and assessments to evaluate the therapeutic efficacy of the third stimulation paradigm. Subjects will express their preference between the three burst stimulation paradigms, their IPGs will be programmed accordingly and they will exit the study.
 
Primary and secondary assessments will be compared between baseline and the two follow up visits.
 
The total duration of the study is expected to be 6 months.
 
The study will be conducted in a maximum of 4 centers in Europe

Devices used:	
Any commercially available SJM neurostimulation system:
 
 
• Implantable Pulse Generator (IPG)
 
• IPG Charger (in case of a rechargeable IPG)
 
• Clinician Programmer
 

Study Population	
The study population will consist of patients with chronic pain for failed back surgery syndrome or neuropathic back and/or leg pain with an implanted commercially available SJM spinal cord stimulation device and have been using conventional burst stimulation parameters for the past three months (Burst train consisting of 5 pulses, Intraburst frequency: 500 Hz, Burst rate: 40 Hz, Pulse width: 1000 μs). Up to 40 subjects will be enrolled in this study in up to 4 centers. Of these, it is expected that 30 subjects will be successfully screened and complete the study.
 
Patients will be considered for enrollment by the Principal Investigator as a candidate for the study at the study site if they meet the inclusion/exclusion criteria requirements, and agree to participate in the study.

Inclusion/Exclusion Criteria	
Inclusion Criteria
 
 
• Subject has been implanted with a commercially available SJM spinal cord stimulator for controlling chronic intractable pain associated with back and/or leg pain;
 
• Subject has been exclusively using burst stimulation for at least three months;
 
• Subject is 18 years of age or older;
 
• Subject’s pain-related medication regimen was stable in the 4 weeks prior to the screening evaluation;
 
• Subject agrees not to add or increase pain-related medication from enrollment through the study duration;
 
• Subject is willing to cooperate with the study requirements including compliance with the regimen and completion of all office visits;
 

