**Clinical Investigational Plan**

[figure not shown]
	
Exclusion Criteria
 
 
• Subject is currently participating in a clinical investigation study that includes an active treatment arm;
 
• Subject is currently receiving, applying or considering seeking workers compensation, or is involved in disability litigation;
 
• Subject has a non SJM neuromodulation device
 

Data Collection	
Subsequent to receiving the informed consent, subjects will be screened for inclusion/exclusion criteria. Eligible subjects will be randomized 1:1:1 to one of the treatment groups and be programmed accordingly. Subjects will be provided with a one-week diary to assess the pain relief provided by the first stimulation paradigm.
 
During the first follow up visit, the subjects will evaluate the pain level experienced during standard burst stimulation using the Visual Analog Scale (VAS), the European Quality of Life-5 Dimension (EQ-5D) questionnaire and the subject satisfaction questionnaire. Subjects will be programmed to the second stimulation paradigm and will be provided with a one-week pain diary.
 
During the second follow up visit, subjects will evaluate the efficacy of the second stimulation paradigm using the same assessments used in the first follow up visit. Subjects be programmed with the third stimulation paradigm and will be provided with a one-week pain diary.
 
During the third follow up visit, subjects will evaluate the efficacy of the last stimulation paradigm using the same assessments used in previous follow up visits. Additionally, subjects will be asked to express their preference between the three stimulation paradigms.
 
Occurrence of adverse events will be recorded through the study duration.

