## 4.4 ENDPOINTS

### 4.4.1 Primary Endpoint

Changes in Visual Analog Scale (VAS) scores between baseline and follow up visits

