## Clinical Investigational Plan

### 6.4 FOLLOW UP VISIT 1

During the baseline visit, the investigator will collect the pain diary provided at the screening visit and record the current stimulation parameters in the parameters form. The subject will rate the pain during the first stimulation paradigm using the VAS, the EQ-5D and the satisfaction questionnaires administered by a clinician blinded to the stimulation paradigm. Subject’s stimulators will be programmed with the second stimulation paradigm according to the group assignment. Stimulation intensity will gradually be increased until the subject perceives the stimulation to find the Threshold for Perception (TP), and then the intensity will subsequently be reduced to the sub-perception level providing optimal pain relief. Subjects will be provided with a new pain diary for the assessment of the new stimulation paradigm. One week after this visit, the subject will be contacted to schedule the second follow up visit and instructed to start recording pain levels on the pain diary

The following activities and assessments will be performed during the first follow up visit.

Timing of visit	Activities at visit	Case Report Form
Follow up 1	
 
Collect pain diary
 
Programming parameters printout
 
Subject fills out pain assessment and quality of life questionnaires
 
Provide pain diary
 
Program IPG with second stimulation paradigm according to group assignment
 
	
 
VAS Form
 
EQ-5D Form
 
User Satisfaction Form
 
Parameters Form
 

### 6.5 FOLLOW UP VISIT 2

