During the second follow up visit, the investigator will collect the pain diary provided at the first follow up visit and record the current stimulation parameters in the parameters form. The subject will rate the pain during the first burst microdosing stimulation paradigm using the VAS, the EQ-5D and the satisfaction questionnaires administered by a clinician blinded to the stimulation paradigm. Subject’s stimulators will be programmed with the third stimulation paradigm according to the group assignment. Stimulation intensity will gradually be increased until the subject perceives the stimulation to find the Threshold for Perception (TP), and then the intensity will subsequently be reduced to the sub-perception level providing optimal pain relief. Subjects will be provided with a new pain diary for the assessment of the new stimulation paradigm. One week after this visit, the subject will be contacted to schedule the third follow up visit and instructed to start recording pain levels on the pain diary

The following activities and assessments will be performed during the second follow up visit:

Timing of visit	Activities at visit	Case Report Form
Follow up 2	
 
Collect pain diary
 
Programming parameters printout
 
Subject fills out pain assessment and quality of life questionnaires
 
Provide pain diary
 
Program IPG with third stimulation
 
	
 
VAS Form
 
EQ-5D Form
 
User Satisfaction Form
 
Parameters Form
 

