#### 12.2 SAMPLE SIZE

Considering the short time required for assessing the outcomes in each subject, we do not expect any drop-out. We will enroll up to 40 subjects, of these 30 are expected to be successfully screened and complete the study. Patients who fail screening will not participate in the study. This study is a feasibility trial, the sample power cannot be calculated because the effect size is not known. The sample size was selected to obtain early evidence and estimates of the effect size.

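### Section 12.1 compares follow-up visits while its hypothesis concerns paradigms; in this rotated crossover, visit contrasts estimate period effects, not paradigm effects

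*Combined protocol and SAP*

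**What the plan says.** The only analysis rule is one sentence in section 12.1. It says that scores "will be compared between follow up visits using a repeated measure ANOVA under the hypothesis of equivalence between standard and burst microdosing stimulation paradigms". No section names a paradigm, period or sequence term.

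The design in section 4.2 and the synopsis is a three-period crossover with 1:1:1 allocation to three sequences. Write S for standard burst, A for 5 s on/5 s off and B for 5 s on/10 s off. Group 1 receives S-A-B, Group 2 A-B-S and Group 3 B-S-A.

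The objectives (sections 4.3.1 and 4.3.2) and the secondary endpoints (section 4.4.2) are framed by paradigm. The primary endpoint is framed by visit: "Changes in Visual Analog Scale (VAS) scores between baseline and follow up visits" in section 4.4.1, and "Change in Visual Analog Scale (VAS) between baseline and follow up visits" in the synopsis. The synopsis design text adds: "Primary and secondary assessments will be compared between baseline and the two follow up visits". There are three follow-up visits.

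Some visit descriptions assume a fixed order:

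- Synopsis, Data Collection: "During the first follow up visit, the subjects will evaluate the pain level experienced during standard burst stimulation".
- Section 6.5, on follow-up visit 2: "The subject will rate the pain during the first burst microdosing stimulation paradigm using the VAS".
- Section 6.4, on follow-up visit 1: "During the baseline visit, the investigator will collect the pain diary provided at the screening visit".

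Other descriptions (the synopsis design text, section 4.2 and section 6.6) correctly tie each visit to the paradigm assigned for that period.

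Section 12.2 gives the purpose of the sample: "The sample size was selected to obtain early evidence and estimates of the effect size".

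**The concern.** In a crossover with rotated sequences, visit and paradigm are different factors. An ANOVA on scores arranged by visit asks whether pain changes over time. The hypothesis in the same sentence asks whether the paradigms differ.

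Two errors could follow. Real differences between paradigms would be averaged out of the comparison, and the resulting null finding could be read as the equivalence that section 3.8 hopes to establish. Conversely, a time trend under identical paradigms could be read as a paradigm difference. In neither case would the analysis give the effect-size estimate for which the sample was chosen.

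**Working it through.** The plan states no power, alpha, SD, effect size or expected time trend, so there is no figure of its own to reproduce. The check is algebra from the sequences, followed by an illustration on assumed values.

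**Inputs from the documents.** Sequences S-A-B, A-B-S and B-S-A with 1:1:1 allocation (section 4.2); 30 completers and no drop-out expected (section 12.2), hence 10 per sequence if balanced.

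**Visit means, equal groups.** Let τ be the paradigm effects and π_v the period effect at visit v. Without carryover, the paradigms delivered are S, A, B at visit 1 (Groups 1, 2, 3), A, B, S at visit 2 and B, S, A at visit 3. Therefore

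E(mean at visit v) = (τ_S + τ_A + τ_B)/3 + π_v.

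The first term is the same at every visit. The contrasts V2−V1, V3−V1 and V3−V2 have paradigm coefficients (0, 0, 0) and equal differences in π only. No assumed SD enters this step.

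**Visit means, unequal groups.** With 12/10/8, the weights on (S, A, B) are (0.400, 0.333, 0.267) at visit 1, (0.267, 0.400, 0.333) at visit 2 and (0.333, 0.267, 0.400) at visit 3. V2−V1 then has coefficients (−2/15, 1/15, 1/15). For effects 0/10/20 mm this is 10/15 + 20/15 = 2 mm. V3−V1 has coefficients (−1/15, −1/15, 2/15), giving −10/15 + 40/15 = 2 mm. The true paradigm contrasts are 10 and 20 mm.

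**Effect on the F test, equal groups.** The paradigm variation does not disappear; it moves into the error term. With effects 0/10/20 mm, each subject contributes (−10)² + 0² + 10² = 200 to the error sum of squares. The error df are (30−1)(3−1) = 58.

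- SD of differences 20 mm: within-subject variance 20²/2 = 200. Expected error mean square 200 + 30×200/58 = 303, against an expected visit mean square of 200.
- SD of differences 30 mm: within-subject variance 30²/2 = 450. Expected error mean square 450 + 103 = 553, against 450.

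The by-visit test should therefore reject less often than 5% when the paradigms truly differ.

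**Simulation.** Assumed: 30 subjects, independent normal errors, no carryover, two-sided 5%, 20,000 replicates. Each cell gives the rejection rate for an SD of differences of 20 mm / 30 mm.

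| Scenario | ANOVA by visit | ANOVA by paradigm |
|---|---|---|
| Effects 0/10/20 mm, no drift | 1.2% / 2.5% | 99.9% / 90.0% |
| Effects 0/5/10 mm, no drift | 3.5% / 4.3% | 66.6% / 34.1% |
| No effect, drift 2 mm per visit | 14.3% / 9.2% | 3.3% to 5.0% across both drift rows |
| No effect, drift 5 mm per visit | 66.7% / 33.6% | as above |
| Groups 12/10/8, effects 0/10/20 mm | 2.1% / 3.4% | 99.9% / 90.1% |

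A model with subject, period and paradigm (56 error df) rejects in 4.7% to 5.3% of trials when there is no paradigm effect and the drift is 0 to 5 mm per visit.

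**Second check on another scale.** Within-subject SD 1, between-subject SD 1.5, 10,000 replicates. With paradigm shifts of 0/0.5/1 SD and no period effect, the by-visit ANOVA rejects in 2.5% and the by-paradigm ANOVA in 93.1%. With period shifts of the same size and no paradigm effect, by visit rejects in 92.9%, and the paradigm-plus-period model in 5.1%. The conclusion does not depend on the millimetre values.

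**The case against.** The strongest reply is that the visit wording is shorthand. Each subject gives one score per paradigm, each score is collected at a follow-up visit, and the hypothesis clause says what is to be contrasted. The objectives, the secondary endpoints and the crossover design support that reading. On it the sentence is coherent, and the only fault is that the ANOVA factor is left unnamed.

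Much of this is fair. Paradigm is clearly the intended comparison. The data would support the right analysis, and nothing in the plan forbids reporting paradigm means. The percentages describe a literal by-visit analysis, not how likely it is to be run. The count of two follow-up visits and the use of the word baseline in section 6.4 are naming slips. The fixed-order wording is inconsistent drafting, not evidence of a different design. What baseline means when Table 1 in section 6.2 schedules no VAS at screening is a separate question, as is the missing equivalence margin. Neither is relied on here.

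The reply still does not settle the matter. No section names paradigm as the factor. The visit framing recurs in the primary endpoint and the synopsis, while the secondary endpoints use paradigm. An analyst who follows the Data Collection text and section 6.5 could treat visit as a label for paradigm, which is right only in Group 1. Feasibility status is no answer either, because estimating the effect is the study's stated purpose.

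**Conclusion.** The point holds and must be fixed: the analysis rule, followed literally, does not address the primary objective. With equal sequence groups and no carryover, the expected visit contrast contributed by paradigms is exactly 0, whatever the true paradigm effect. With 12/10/8 it is at most 2 mm when the paradigms differ by 10 and 20 mm. Carryover would contaminate visit contrasts further and would not turn them into paradigm contrasts.

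The cancellation follows from the design alone. The rejection rates rest on assumed SDs, effects, drift and a millimetre scale, none of which the documents give, and serve only to show scale.

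**What to change.** Required:

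- In section 12.1, state that scores are compared between the three stimulation paradigms, with paradigm as the within-subject factor.
- Restate the primary endpoint (section 4.4.1 and synopsis) and the synopsis sentence on comparing assessments by paradigm. Any common pre-treatment baseline cancels from the within-subject paradigm contrasts.
- Reconcile the synopsis Data Collection text and sections 6.4 and 6.5, so that each visit assesses the paradigm assigned for that period and follow-up visit 1 is not called baseline.

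Preferred but not essential: a mixed model with paradigm and period (optionally sequence) as fixed effects and subject as random, reporting A minus S and B minus S with confidence intervals.

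Cost: wording only, with no change to data, visits or sample size. Adding period takes 2 error degrees of freedom (58 to 56 at 30 subjects). In the simulation with equal groups and no drift, power changed by at most 0.2 percentage points.
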